10.4 Stopping Rule

The study will be monitored to ensure that the occurrence of a specified set of treatment related serious adverse events (TRSAEs) during the subsequent weeks (18-70) of intervention does not substantially exceed an anticipated rate. The following TRSAEs will be considered for early stopping of either one of groups A or B:

- Death considered to be probably or definitely related to the inhaled CsA or
- Any grade IV toxicity considered to be probably or definitely related to inhaled CsA, i.e. opportunistic infection such as tissue-invasive CMV or *Pneumocystis carinii*, with exception of temporary cytopenias.

We will monitor the numbers of subjects who have developed any of the above-specified TRSAEs using the stopping rule outlined below. The trial will be seriously considered for early stopping if the number of subjects in the trial who develop TRSAEs is over the pre-specified threshold value in the Table.

From experience using this agent in other clinical settings as detailed in the investigator's brochure, we anticipate the rate of developing at least one of the above-specified TRSAEs to be 10% or less. Following Geller et al., our stopping rule is determined by a Bayesian approach²³. The stopping boundary for the trial is reached if the Bayesian posterior probability that the true probability of developing one or more of the above-specified TRSAEs exceeds this benchmark rate of 10% is at least 90%. We take our prior distribution to be a beta distribution with the sum of the two beta

parameters to be 3, i.e. the parameters of the beta prior distribution are 0.30 and 2.70. Since we have seen in the past that the first few subjects to be accrued are possibly sicker than the rest of the subjects in the sample, we will start safety monitoring when 3 subjects have developed specified SAEs. The following table summarizes the threshold numbers for stopping either group A or B:

Number of Subjects	Stop if the number of subjects who develop any of the number of specified TRSAEs reaches:
≤ 11	3
$12 \leq n \leq 18$	4
$19 \leq n \leq 25$	5
$26 \leq n \leq 32$	6
$33 \leq n \leq 39$	7

We investigated the performance of the above stopping rules by a simulation study. For the stopping rule, we generated a study with 39 independent Bernoulli trials, each had a probability $p=.1$ for having the above TRSAE and $q=1-p$ for not having such TRSAE and compared the TRSAE outcomes with the above stopping boundary to determine whether the study was stopped. We repeated the simulation 100,000 times and computed the proportion of stopped studies (i.e. “number of stopped studies”/100,000), which were stopped using the above stopping rule.

The following table summarizes the proportions of stopped studies under a number of scenarios.

Prob of specified TRSAE	5%	10%	15%	20%	30%
Proportion of Stopped Studies	2.2%	20.2%	51.5%	77.4%	98.1%
Average Number of Subjects	38.4	34.5	27.8	21.0	11.9
Average Number of Subjects Suffering TRSAE	1.93	3.47	4.18	4.18	3.54

The DSMB will evaluate all serious adverse events and have all the required information to implement the above-defined monitoring plan. In addition, the DSBM may recommend early study termination if other unforeseen adverse events necessitate this decision.

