13.4 Risks in relation to benefits

13.4.1 For Adult Subjects

The risks of participating in this trial are limited to side effects of the albuterol/levalbuterol and inhaled CsA, and the risks of standard diagnostic procedures (BAL and biopsy, the high resolution CT, and pulmonary function tests), the 6 minute walk, and the additional peripheral blood sample to be used strictly for research purposes. Samples for clinical monitoring will be collected during sample collection procedures that are part of their routine post transplant care and therefore pose no additional burden or risk.

The benefits to the subjects could be improvement in BO resulting in improved quality of life, decreased mortality associated with severe BO (should it develop), and potentially, treatment with other more toxic systemic therapies could also be avoided or postponed. Subjects will also receive direct health benefits due to thorough post transplant pulmonary examinations, early diagnosis of progression of BO and therefore earlier access to appropriate BO management. Therefore, for adult subjects participating on this study, the research involves greater than minimal risk to subjects with the prospect of direct benefit (45 CFR 46.102).

As of May 10, 2019, this study is now closed to new subject accrual and continues in data analysis and/or sample analysis only and the level of risk is now minimal.

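### Section 10.4 words the TRSAE stopping trigger two ways, one affected subject apart; only the table's *reaches* fits the plan's 90% criterion and its printed operating characteristics

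*Combined protocol and SAP*

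**What the plan says.** All of the relevant text is in section 10.4 of the combined protocol and SAP. It applies to group A (stem cell recipients) and group B (lung recipients) separately.

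- The introductory sentence considers stopping "if the number of subjects in the trial who develop TRSAEs is over the pre-specified threshold value in the Table".
- The header of the threshold table reads "Stop if the number of subjects who develop any of the number of specified TRSAEs reaches". The listed numbers are 3 (n ≤ 11), 4 (12–18), 5 (19–25), 6 (26–32) and 7 (33–39).
- The formal definition is Bayesian: "The stopping boundary for the trial is reached if the Bayesian posterior probability" that the true event rate "exceeds this benchmark rate of 10% is at least 90" per cent. For the prior, "the parameters of the beta prior distribution are 0.30 and 2.70". Monitoring starts once three subjects have had a qualifying event.
- The operating characteristics come from 100,000 simulated studies of 39 subjects each, which "compared the TRSAE outcomes with the above stopping boundary to determine whether the study was stopped".
- The DSMB is to "have all the required information to implement the above-defined monitoring plan".

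No other section reconciles the two wordings. Section 12.3 only refers back to 10.4.

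**The concern.** The sentence and the table header use the same numbers but differ by one affected subject at every sample size. The qualifying events are deaths and grade IV toxicities attributed to the inhaled drug, so one event of delay is not trivial. If the sentence had been followed, each group would have come up for stopping one affected subject later than the posterior criterion requires. The printed operating characteristics would then describe a different rule from the one in use.

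**Working it through.** **Inputs, all from section 10.4.** Prior Beta(0.30, 2.70); benchmark rate 10%; criterion posterior ≥ 0.90; monitoring from 3 events; at most 39 subjects per group; table values 3/4/5/6/7; printed operating characteristics at true rates of 5, 10, 15, 20 and 30%.

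**Step 1: reproduce the table.** With s affected subjects among n, the posterior is Beta(0.30 + s, 2.70 + n − s). The boundary is the smallest s ≥ 3 for which P(rate > 0.10) ≥ 0.90. For n = 3 to 39 this equals the printed table at every n. The floor of 3 matters only at n = 3 to 5, where two events would already give 0.956, 0.933 and 0.907.

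**Step 2: posterior on either side of the table value, at the last n of each row.**

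| n | table value | one fewer | at table value | one more |
|---|---|---|---|---|
| 11 | 3 | 0.713 | 0.9082 | 0.9786 |
| 18 | 4 | 0.746 | 0.9028 | 0.9705 |
| 25 | 5 | 0.774 | 0.9041 | 0.9662 |
| 32 | 6 | 0.797 | 0.9081 | 0.9643 |
| 39 | 7 | 0.817 | 0.9131 | 0.9639 |

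At the first n of rows two to five (12, 19, 26, 33), one fewer event gives 0.889, 0.887, 0.891 and 0.897, still below 0.90. The table values are therefore the counts at which the criterion is first met. Under *over*, the lowest posterior at which stopping can occur is 0.964 (8 of 39).

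**Step 3: operating characteristics.** Exact forward recursion over 39 independent Bernoulli subjects, checking the boundary after each one. *Reaches* stops at the table value; *over* stops at the table value plus 1.

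| True rate | 5% | 10% | 15% | 20% | 30% |
|---|---|---|---|---|---|
| Stopped, printed | 2.2% | 20.2% | 51.5% | 77.4% | 98.1% |
| Stopped, *reaches* | 2.5% | 19.5% | 50.5% | 77.9% | 98.2% |
| Stopped, *over* | 0.4% | 7.2% | 29.8% | 60.4% | 94.9% |
| Mean subjects, printed | 38.4 | 34.5 | 27.8 | 21.0 | 11.9 |
| Mean subjects, *reaches* | 38.4 | 34.7 | 28.0 | 21.0 | 11.8 |
| Mean subjects, *over* | 38.9 | 37.7 | 33.9 | 27.9 | 16.9 |
| Mean affected, printed | 1.93 | 3.47 | 4.18 | 4.18 | 3.54 |
| Mean affected, *reaches* | 1.92 | 3.47 | 4.20 | 4.19 | 3.53 |
| Mean affected, *over* | 1.95 | 3.77 | 5.08 | 5.58 | 5.06 |

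Against the printed proportions, *reaches* is off by at most 1.0 percentage point. *Over* is off by 13.0 points at 10%, 21.7 at 15%, 17.0 at 20% and 3.2 at 30%. At 5% both are close in absolute terms, and the other columns decide.

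**Step 4: how good the match is.** The simulation standard error is √(P(1 − P)/100,000), about 0.13 point at a 10% rate. Printed minus exact *reaches* is −5.3, +5.5, +6.1, −3.8 and −1.8 standard errors across the five rates. The match is close but not exact, and the documents do not explain the remainder.

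**Step 5: cost of the later trigger at a 20% rate.** Subjects: 27.9 − 21.0 = 6.9 more. Affected: 5.58 − 4.19 = 1.39, about 1.4 more.

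**The case against.** The strongest reply is that nothing is miscalculated. The table is the correct output of the stated prior and criterion, and the loose sentence sends the reader to the rule below it, where everything points to *reaches*. The sentence is also advisory in tone, so a DSMB working from the table would apply the intended rule. That is fair, and it is why the intended trigger is not in doubt. It does not remove the contradiction, because the sentence is current text and gives the opposite instruction at the boundary count.

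Counts above the table also satisfy the 90% criterion. This too is correct: *over* acts late rather than without support. Late action is still not the stated rule.

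The figures of 6.9 subjects and 1.4 affected assume that each subject's outcome is known before the next is counted. Section 10.4 monitors events over weeks 18 to 70, and section 11.1 leaves the review interval to the DSMB, so these are not forecasts of real exposure. They use the same idealisation as the plan's own simulation and should be read only in that setting.

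The practical consequence is limited. Section 10.4 also lets the DSMB recommend termination for other unforeseen adverse events. Section 13.4.1 states that "this study is now closed to new subject accrual and continues in data analysis and/or sample analysis only". Nothing in the documents suggests that *over* was applied or that any count came near a boundary.

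Separately, section 10.4 counts events probably or definitely related to the drug, while section 12.3 adds those possibly related. That conflict affects what is counted, not the trigger, but any reported count must say which attribution it used.

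**Conclusion.** The concern holds. Section 10.4 gives one safety boundary two triggers, and the sentence is the outlier: the table header, the posterior definition and the printed operating characteristics all agree with *reaches*. Read literally, the sentence raises the effective posterior threshold from 0.90 to at least 0.964. It cuts the chance of stopping from 50.5% to 29.8% at a true rate of 15%, and from 77.9% to 60.4% at 20%. The boundary result needs only the stated prior, criterion and three-event start. The operating characteristics also assume independent subjects and a check after each one. With accrual closed, this should be corrected for the record and for reporting; no enrolment decision now depends on it.

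**What to change.** In section 10.4, replace *is over* with *reaches (is equal to or greater than)*, so that the sentence agrees with the table header and the 90% criterion. In the study report, state:

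- which trigger was applied in monitoring;
- the TRSAE count and number of subjects per group at each DSMB review, with the attribution categories counted;
- whether any count equalled the table value.

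The cost is one phrase in the plan and a short statement in the report. No table value changes, and no new data or simulation is needed to correct the wording.

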10.5 Off Study Criteria

10.5.1 Patient choice: Subjects may withdraw from the study at their request any time. The risks of withdrawing will be discussed, as will alternative treatment options. Those subjects who choose to withdraw will be strongly encouraged to participate in study assessments until he/she initiates alternative BO therapy. In this scenario, patients will be deemed off study-drug, but have the option to continue on-study.

10.5.2 Principal investigator decision:

Subjects will be taken off study drug during study if:

- Subject demonstrates disease progression, as defined by
 - a 20% or more decline in FEV₁ on two successive measurements at least two weeks apart or

- an increase in the existing dose of one or more immunosuppressive therapies by at least 25% above baseline levels from the primary protocol due to worsening BO/BOS (sustained for 3 weeks, excluding adjustments made for target drug levels) or
- subject requires the addition of new immunosuppressive therapies (sustained for 3 weeks) due to worsening symptoms related to BO/BOS.
- Evidence of an NCI grade IV toxicity related to study drug administration.
- Worsening performance status, defined by ECOG score ≥ 3 (please see hematology supportive care guidelines).
- Disease relapse or a significant non-pulmonary transplant complication in which death is likely to occur and prohibit administration of CIS.
- Patients that have had their CIS tapered off with no worsening of PFTs in the subsequent 12 months.
- Inability to comply with the study visits or become severely ill and cannot comply with the intervention.
- Are unable to tolerate the 150 mg dose of the inhaled CsA.
- Develop severe pulmonary infection that fails to respond to conventional treatment or where no treatment exists.
- Subject becomes pregnant.

These subjects will be asked to complete the end of study assessments, as off-study drug participants, after which they will be referred back to their primary transplant team.

10.5.3 Completion of the study

Upon completion of the off study assessments, subjects will have completed study participation and be taken off study and referred back to their primary transplant team to continue post transplant monitoring and care.

11.0 DATA AND SAFETY MONITORING PLAN

11.1 Safety Monitoring

Principal Investigator: Accrual, efficacy and safety data will be monitored by the Principal Investigator, [name] and [name]., Medically Responsible Investigator.

NIH Intramural IRB. Accrual and safety data will be monitored and reviewed annually by the Institutional Review Board (IRB). Prior to implementation of this study, the protocol and the proposed patient consent and assent forms will be reviewed and approved by the properly constituted Institutional Review Board (IRB) operating according to Title 45 CFR 46. This committee will also approve all amendments to the protocol or informed consent, and conduct continuing annual review so long as the protocol is open to accrual or follow up of subjects.

NHLBI DSMB: The NHLBI Data Safety and Monitoring Board will review the protocol at an interval to be determined by the DSMB. A progress report will be forwarded to the DSMB at these times and their recommendations will be expeditiously implemented. The DSMB may recommend early termination of the study for considerations of safety and efficacy.

FDA: An annual progress report, any amendments to the protocol, and any change in the status of the protocol will be forwarded to FDA to:

[name], Regulatory Officer
 [name], Division Director
 Division of Special Pathogen and Transplant Products Central Document Room Center of
 Drug Evaluation and Research, FDA
 [name] [name] 20705 (w) [contact]

APT Pharmaceuticals, Inc.: An copy of the annual progress report to FDA, any amendments to the protocol, and any change in the status of the protocol will be forwarded to

[name] [[contact]]
 APT Pharmaceuticals, Inc
 [name]
 Telephone Number Fax Number

NIH Radiation Safety Committee (RSC): Because the frequency of CT imaging exceeds that which is standard in this patient population, some of the radiation exposure is therefore determined as indicated for research purposes. The Radiation Safety Form 88-23a which, includes dosimetry calculations for the high resolution CT scans, has been submitted to the Radiation Safety Committee and approved (c/o [name]., Clinical Protocol Administrator, NIH Radiation Safety Committee [contact]) for initial and triennial RSC review so long as the protocol remains open for patient accrual and intervention.

	Baseline	On CIS				After wk 70	
PROTOCOL TIMEPOINT	Wk 18	Wk 30	Wk 42	Wk 54	Wk 70	Every 6-12 weeks*	End of study
High resolution chest CT *if clinically indicated						* 	

Data management: The PI will be responsible for overseeing entry of data into an in-house password protected electronic system and ensuring data accuracy, consistency and timeliness. The principal investigator, associate investigators, research nurses and/or a contracted data manager will assist with the data management efforts. Data will be abstracted from Clinical Center progress notes as well as from progress notes forwarded from home physicians. Laboratory data from NIH will be imported electronically from CRIS into an in-house clinical trial database. Laboratory values from referring home physicians will be entered into the system.

In order to maintain patient confidentiality, all case report forms, study reports and communications relating to the study will identify patients by assigned patient numbers. Case report forms may serve as source data if needed. All human subjects personally identifiable information (PII) as defined in accordance to the Health Insurance Portability and Accountability, eligibility and consent verification will be recorded. Primary data obtained during the conduct of the protocol will be kept in secure network drives or in approved alternative sites that comply with NIH security standards. Primary and final analyzed data will have identifiers so that research data can be attributed to an individual human subject participant, e.g. a unique code, or minimum PII required for subject identification. All primary and analyzed data will be located on the secure P drive.

In accordance with local and federal regulations, the Investigator will allow APT Pharmaceuticals, Inc. personnel or their designee, access to all pertinent medical records in order to verify the data gathered on the case report forms and to audit the data collection process. The US Food and Drug Administration (FDA) may also request access to all study records, including source documentation for inspection.

End of study procedures: Data will be stored in locked cabinets and in a password protected database until it is no longer of scientific value. Federal law requires that an Investigator maintain all study records for the indication under investigation for two years following the date a Product Licensing Application is approved or, if no application is to be filed or if the application is not approved for such indication, until two years after the investigation is discontinued and the FDA is notified.

Clinical Trial Monitoring Plan: Monitoring Responsible Party/ Monitor: An experienced independent protocol monitoring group has been contracted by the NHLBI. They will objectively audit records for compliance with the protocol.

Monitoring will assure the adequate protection of human subjects, safety of subjects involved in clinical investigations and the integrity and quality of data. The monitor/ responsible party for monitoring will be trained to perform monitoring activities.

Monitoring may occur prior to the IRB approval of the study (protocol/ site initiation), routine monitoring (during the protocol life cycle), and study termination. The monitoring activities will verify regulatory compliance, NIH & DIR policy compliance, IRB regulatory compliance, subject record review, and protocol compliance. The monitoring activities will be documented and the reports will be made available to regulatory personnel.

Loss or destruction of data: Should we become aware that a major breach in the our plan to protect patient confidentiality and trial data has occurred, the IRB will be notified.

Publication Policy: Given the research mandate of the NIH, patient data including the results of testing and responses to treatment will be entered into an NIH-authorized and controlled research database. Any future research use will occur only after appropriate human subject protection institutional approval such as prospective NIH IRB review and approval or an exemption from the NIH Office of Human Subjects Research (OHSR).

12. ADVERSE EVENTS

12.1 Definitions

Adverse Event (AE): Any untoward or unfavorable medical occurrence in a human subject, include any abnormal sign (e.g. abnormal physical exam or laboratory finding), symptom, or disease, temporally associated with the subject's participation in the research, whether or not considered related to the research. AE data are recorded on the CRF. The Principal Investigator or a physician member of the research team and the study coordinator will assess each participant for any new or continuing adverse events.

An abnormal laboratory value will be considered an AE if the laboratory abnormality is characterized by any of the following:

- Results in discontinuation from the study

- Is associated with clinical signs or symptoms
- Requires treatment or any other therapeutic intervention
- Is associated with death or another serious adverse event, including hospitalization
- Is judged by the Investigator to be of significant clinical impact
- If any abnormal laboratory result is considered clinically significant, the investigator will provide details about the action taken with respect to the test drug and about the patient's outcome.

Serious Adverse Events (SAE): A serious adverse event: Any adverse event that:

- results in death;
- is life-threatening (places the subject at immediate risk of death from the event as it occurred);
- results in inpatient hospitalization or prolongation of existing hospitalization.
- results in persistent or significant incapacity.
- results in a congenital anomaly/birth defect; or based upon appropriate medical judgment, may jeopardize the subject's health and may require medical or surgical intervention to prevent one of the other outcomes listed in this definition.

Serious event: An event is serious if it meets the definition of a serious adverse event (above) or if it requires immediate corrective action by a PI and/or IRB to protect the safety, welfare or rights of subjects.

Unanticipated problem that is not an Adverse Event (UPnonAE): An unanticipated problem that does not fit the definition of an adverse event, but which may, in the opinion of the investigator, involves risk to the subject, affect others in the research study, or significantly impact the integrity of research data. For example, report occurrences of breaches of confidentiality, accidental destruction of study records, or unaccounted-for study drug.

Protocol Deviation (PD): Any change, divergence, or departure from the IRB approved study procedures in a research protocol that does not have a major impact on the subject's rights, safety or well-being, or the completeness, accuracy and reliability of the study data.

Unanticipated Problem (UP): Any incident, experience, or outcome that is:

1. unexpected in terms of nature, severity, or frequency in relation to
 - a. the research risks that are described in the IRB-approved research protocol and informed consent document; Investigator's Brochure or other study documents; and
 - b. the characteristics of the subject population being studied; and
2. related or possibly related to participation in the research; and
3. places subjects or others at a greater risk of harm (including physical, psychological, economic, or social harm) than was previously known or recognized.

